10.3 Sample Size and Study Outcome Determination

A precision approach will be used to determine the appropriate sample size and power for the study. For power and sample size considerations a type 1 error rate (alpha) of 0.05, one-sided, will be used. Given a sample size of 50 the calculations have been done with various standard deviations to show power below and above 90% (see Table 1 below). Sixty to seventy participants will be enrolled to allow for the fifty per-protocol participants, although the analyses will be done on the mITT population.

The assumptions made for the power and sample size computations come from the Poise study (Ziv et al), where their assumption for the effect size was reduction in pad weight gain per 8 hours of 70%, with a standard deviation of 15%. The results of the study showed an 86% reduction in pad weight gain per 8 hours with a 9% standard deviation. Given those results, this study's assumptions of 60% improvement and a range of standard deviations from 15% to 20% appear conservative; thus, the expected results would indicate a successful outcome for the primary endpoint.

The computations below are based on the precision method, which in the case of this study computes a lower 95% confidence limit for the percentage change. Here we consider a changes around 60% in the explanation of the table. Different standard deviations are used with the sample size of 50.

Table 1.

n	½ width of CI	Std Dev	Power
50	5	16	0.999
50	5	17	0.991
50	5	18	0.956
50	5	19	0.869
50	5	20	0.720
50	6	20	0.995

The first entry in the table shows that if the resulting mean reduction in pad weight gain was 60% and the standard deviation of the mean percentage change was 16%, the lower limit of the 95% confidence interval for 60% would be 55%: 60% - 5% (½ width), with 99.9% probability (power). The last line in the table above shows that the resulting mean percentage change would have to be greater than 56 for the power to be 99.5% (56% - 6% ½ width = 50%, not greater than 50%) if the standard deviation was 20%. If the result was 60% the lower limit of the confidence interval would be 54%: (60% - 6%) with 99.5% power. Thus, for all lines above except 4 and 5 the endpoint was reached with greater than 90% power.

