A successful outcome for this endpoint would be any result where the lower limit of the 95% confidence interval is above 50% with more than 90% power, as explained above. When the results are tabulated, another table will be created with the n's and standard deviations from the study for comparison to the study results.

Also, this sample size should also be sufficient for inferential analysis of the secondary endpoints.

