10.4 Statistical Hypotheses and Data Description

1. Type 1 Error and Multiplicity Concerns:

The inferential tests for the one primary and two secondary endpoints were initially conceived to be one-sided using alpha=0.05. Since the sponsor wishes to use the success of all three for labeling and marketing purposes, a Bonferroni adjustment for multiple comparisons will be employed. Thus, statistical significance will be indicated for each endpoint if the p-value is less than 0.0167.

2. Primary Endpoint:

There is one primary endpoint, for efficacy. The objective is to show that reduction in the mean pad weight gain per hour is >50% in the treatment period. Thus, the null hypothesis is that the mean weight gain reduction per hour is <=50%, and the alternative is that it is >50%, from the control period (no device) to the treatment period (women wearing the device). The data values will be computed for each woman as:

[(total weight of all pads worn during the treatment period/hrs. pads are worn during treatment)

minus

(total weight of all pads worn during the control period/ hrs. pads are worn during control)]

The above quantity divided by
(total weight of all pads worn during the control period/ hrs. pads are worn during control)

This resulting quantity is then multiplied by 100.

Ex. Subject's total pad weight for control period is 140 grams. Pads were worn for a total of 100 hours. Weight/hr. is $140/100 = 1.4$ g/hr. Subject's total pad weight for treatment period is 60 grams. Subject wore pads for 100 hours. Pad weight per hour is $60/100 = 0.6$ g/hr. Difference, treatment – control is $0.6 - 1.4 = -0.8$ g/hr. For the percent change, $100 * (-0.8/1.4) = -57.143\%$. Therefore the reduction in pad weight gain is 57.143%.

The null hypothesis will be that the mean reduction in pad weight gain per hour is less than or equal to 50%, with the alternative that it is greater than 50%. If the raw percentage change data appear to be normally distributed, a paired t-test will be used to test the hypothesis. If not, see section 10.6 (2).

The precision method will be utilized to determine success. The precision approach creates a lower bound for a confidence interval that is higher than the reference, in this case 50%. This 50% standard was chosen based on the FDA guidance document.

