- b. For the quality of life score there will be three measures as described in the visit schedule above. For descriptive purposes the results and change from the previous visit will be shown, as well as the change from the enrollment visit to the post-treatment visit. The changes will likely be negative scores as the QOL is expected to improve, as the instrument records lower numbers as indicating a better quality of life. For the purposes of inferential analysis, a mixed model analysis of variance on the scores will be used on the result at time t (t=baseline, post-control, post-treatment) with time as a fixed effect and subject as a random effect. Thus, the null hypothesis is that there is no significant difference from baseline/enrollment to post-treatment, i.e., that the mean change in score is 0. The alternative is that this change is less than 0. Correlation of scores within subjects will be considered as compound symmetric. The p-value indicating the significance of the least square mean score at the third time-point compared to that at the first time-point will determine if the endpoint is met.

All inferential testing will be done on the mITT population and will be one-sided. As noted above statistical significance will be reached if the relevant p-value is less than 0.0167. Results for all populations will be reported.

There is a secondary safety endpoint as described earlier in the protocol. Safety reporting using urinalysis, vaginal swab, vaginal examination, and evaluation will be descriptive and narrative in nature.

Similarly, exploratory endpoint results of comfort and successful use will be descriptive. No inferential hypotheses will be used here.

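### The Power column of Table 1 gives the chance of a narrow confidence interval, not the power to show a reduction above 50%, yet section 10.3 reads it as endpoint power and writes it into the success rule

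*Combined protocol and SAP*

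**What the plan says.** Section 10.3 announces a precision approach and states that "a type 1 error rate (alpha) of 0.05, one-sided, will be used". It fixes n at 50 and varies the SD, and the planning assumptions are described this way: "assumptions of 60% improvement and a range of standard deviations from 15% to 20% appear conservative". Table 1 lists six lines (half-width/SD): 5/16, 5/17, 5/18, 5/19, 5/20 and 6/20. Its last column, headed Power, reads 0.999, 0.991, 0.956, 0.869, 0.720 and 0.995.

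The text works through the first and last lines. For the last it says that "the resulting mean percentage change would have to be greater than 56 for the power to be 99.5" per cent. It then concludes: "Thus, for all lines above except 4 and 5 the endpoint was reached with greater than 90% power". The section goes on to define success as "any result where the lower limit of the 95% confidence interval is above 50% with more than 90% power", and promises a second table built from the n and SD that the study observes.

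Section 10.4 sets the null hypothesis at a mean reduction of 50% or less. After a Bonferroni adjustment, "statistical significance will be indicated for each endpoint if the p-value is less than 0.0167", and "All inferential testing will be done on the mITT population and will be one-sided". Its primary endpoint item again compares the result with the scenarios of section 10.3 and refers to adequate power.

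**The concern.** Power against 50% must depend on how far the true mean lies from 50%. A column that does not use that distance cannot be power for this endpoint, whatever its heading. Lines 5 and 6 have the same n and SD and differ only in the chosen half-width, yet they carry 0.720 and 0.995. That is proper for a width probability and impossible for the power of one test.

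Two things are at stake. Table 1 is the plan's only justification of the sample size, so a planner could take from it the wrong mean for a safe trial. The label also reaches the decision rule: success needs a lower limit above 50% and, in addition, more than 90% on this column. That second condition depends on which half-width is chosen, possibly after the data are in.

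**Working it through.** **Inputs.** From section 10.3: n=50, one-sided 0.05, planning mean 60%, SD 16 to 20 in Table 1, half-widths 5 and 6. From section 10.4: reference 50%, one-sided 0.0167, and a paired t-test on each woman's percentage change, which is a one-sample t-test of the reductions against 50%. With 49 degrees of freedom the critical values are t=1.6766 (0.05) and t=2.1889 (0.0167).

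**Step 1: reproduce Table 1.** The half-width is t·s/√50, where s is the sample SD. For true SD σ,

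P(half-width ≤ h) = P(χ²₄₉ ≤ 49·50·h²/(t²·σ²)).

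For line 1 the bound is 49·50·25/(1.6766²·256) = 85.1, which gives 0.999. The same probability conditional on the interval covering the true mean was found by simulation (2,000,000 trials per line).

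| Line | h / SD | Stated | Formula | Conditional on coverage |
|---|---|---|---|---|
| 1 | 5/16 | 0.999 | 0.999 | 0.999 |
| 2 | 5/17 | 0.991 | 0.991 | 0.991 |
| 3 | 5/18 | 0.956 | 0.957 | 0.956 |
| 4 | 5/19 | 0.869 | 0.872 | 0.869 |
| 5 | 5/20 | 0.720 | 0.726 | 0.720 |
| 6 | 6/20 | 0.995 | 0.995 | 0.995 |

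The conditional form matches every line to three decimals. A two-sided 0.05 interval (0.850, 0.659, 0.438, 0.250, 0.125, 0.730) does not match. Neither 60% nor 50% appears in the formula.

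**Step 2: power of the planned test.** Power = P(T > t), with T non-central t on 49 df and non-centrality (μ − 50)/(σ/√50). At μ=60 and σ=20 the non-centrality is 10/2.828 = 3.54.

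| SD | Power at μ=60, 0.05 | Power at μ=60, 0.0167 |
|---|---|---|
| 16 | 0.997 | 0.986 |
| 17 | 0.993 | 0.973 |
| 18 | 0.987 | 0.956 |
| 19 | 0.979 | 0.934 |
| 20 | 0.967 | 0.908 |

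Lines 4 and 5 (SD 19 and 20) are above 90% at both levels.

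**Step 3: the 56% threshold.** At a true mean of 56% and SD 20 the non-centrality is 6/2.828 = 2.12. Power is 0.67 at 0.05 and 0.48 at 0.0167. At SD 20, 90% power needs a true mean of about 58.4% (59.9% at 0.0167).

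**Step 4: line 1 with the mean left free to vary.** With true mean 60% and SD 16, the chance that the lower limit is at least 55% is 0.70. The 0.999 holds only once the observed mean is fixed at 60%.

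**Step 5: the success rule.** Take an observed mean of 60%, SD 20, n=50. The lower limit is 60 − 1.6766·20/√50 = 60 − 4.74 = 55.3%. At the 0.0167 level it is 60 − 2.1889·20/√50 = 60 − 6.19 = 53.8%. Both exclude 50%. The added condition of more than 90% fails by line 5 (0.720) and is met by line 6 (0.995). If Table 1 is rebuilt at the 0.0167 level, its lines become 0.564, 0.334, 0.167, 0.073, 0.028 and 0.405, and none reaches 90%.

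**The case against.** The best defence is that section 10.3 names the precision method openly, and that its worked sentences are conditional on the resulting mean. Read that way, 99.9% and 99.5% are correct probabilities that the lower limit is at least 55% or 54%. This stands, and it rules out several stronger readings that a reader might infer.

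- **That every power statement in 10.3 is wrong.** The documents do not support this. Besides the conditional sentences, the claim of more than 90% is numerically true as test power for lines 1, 2, 3 and 6 at a true mean of 60%, at both levels.
- **That the plan claims 99.5% power at a mean of 56%.** It says the resulting mean must exceed 56, and notes that exactly 56 gives a lower limit of 50%, which is not above 50%. The 0.67 in Step 3 concerns a true mean of 56%, which is a different question. It shows what a planner would lose by taking the figure as power.
- **That Table 1 contradicts itself.** Lines 5 and 6 use different half-widths and both reproduce. They conflict only when the column is read as power.
- **That 50 women are too few.** At the planning mean, power is at least 0.908 across Table 1's SDs.

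The defence does not rescue the closing sentence, which speaks of the endpoint being reached with a given power, or the success rule, which makes that figure a condition.

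**Conclusion.** Wrong as written. The column is a width probability that leaves out the sampling error of the mean, and the plan uses it as endpoint power in two places. In the closing sentence the error is conservative, since it denies lines 4 and 5 the 90% that they have. A true mean just above 56% with SD 20 would be taken as far safer than it is. The effect on the success rule is the more serious one: a result that clearly rejects 50% can be called a success or a failure according to the half-width chosen.

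The power figures assume normally distributed percentage reductions and 50 women analysed. Section 10.3 plans 60 to 70 enrolled for 50 per protocol and analyses the mITT population, so the analysed number may be somewhat larger and power somewhat higher. The design, the hypothesis and the sample size are not in question at a true mean of 60%.

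**What to change.** 1. In Table 1, rename the last column: probability that the half-width does not exceed x.
2. Add a table of one-sample t-test power against 50%, at one-sided 0.0167, for n=50, true means of 55% to 65% and SDs of 15 to 20.
3. Delete or reword the sentence on a mean greater than 56 and the sentence that excludes lines 4 and 5.
4. In the success definition that closes section 10.3, remove the condition of more than 90% power. In the primary endpoint item of section 10.4, remove the comparison with the section 10.3 parameters and the wording on adequate power. Success is then a lower confidence limit above 50%, at the level used for the primary test.
5. Keep n=50.

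The cost is protocol and SAP wording and one recalculated table. No extra participants are needed.

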10.4 Statistical Hypotheses and Data Description

1. Type 1 Error and Multiplicity Concerns:

The inferential tests for the one primary and two secondary endpoints were initially conceived to be one-sided using alpha=0.05. Since the sponsor wishes to use the success of all three for labeling and marketing purposes, a Bonferroni adjustment for multiple comparisons will be employed. Thus, statistical significance will be indicated for each endpoint if the p-value is less than 0.0167.

2. Primary Endpoint:

There is one primary endpoint, for efficacy. The objective is to show that reduction in the mean pad weight gain per hour is >50% in the treatment period. Thus, the null hypothesis is that the mean weight gain reduction per hour is <=50%, and the alternative is that it is >50%, from the control period (no device) to the treatment period (women wearing the device). The data values will be computed for each woman as:

[(total weight of all pads worn during the treatment period/hrs. pads are worn during treatment)

minus

(total weight of all pads worn during the control period/ hrs. pads are worn during control)]

The above quantity divided by
(total weight of all pads worn during the control period/ hrs. pads are worn during control)

This resulting quantity is then multiplied by 100.

Ex. Subject's total pad weight for control period is 140 grams. Pads were worn for a total of 100 hours. Weight/hr. is $140/100 = 1.4$ g/hr. Subject's total pad weight for treatment period is 60 grams. Subject wore pads for 100 hours. Pad weight per hour is $60/100 = 0.6$ g/hr. Difference, treatment – control is $0.6 - 1.4 = -0.8$ g/hr. For the percent change, $100 * (-0.8/1.4) = -57.143\%$. Therefore the reduction in pad weight gain is 57.143%.

The null hypothesis will be that the mean reduction in pad weight gain per hour is less than or equal to 50%, with the alternative that it is greater than 50%. If the raw percentage change data appear to be normally distributed, a paired t-test will be used to test the hypothesis. If not, see section 10.6 (2).

The precision method will be utilized to determine success. The precision approach creates a lower bound for a confidence interval that is higher than the reference, in this case 50%. This 50% standard was chosen based on the FDA guidance document.

Power and sample size calculations determine scenarios of success. When the resulting mean reduction in pad weight gain per hour is quantified, its lower limit of a $(1-0.0167)\%$ confidence level is determined. This value is then compared to parameters determined to be efficacious in the sample size calculations (section 10.3). It is expected that the mean reduction per hour will be >50% such that the lower limit of the confidence interval for that result will be higher than 50% with adequate power to suggest success for the study.

3. Secondary Endpoints:

- a. For the change in SUI episodes endpoint each subject will have a change in the number of episodes per day from the control period to the treatment period. Specifically, the number of episodes will be recorded each day in the diary. For the control phase, there will be (at most) 7 days of data. The mean number of SUI episodes per day will be computed for each subject. The same measures

will occur in the treatment period for the analysis period, the last 7 days. Each subject will again have a mean number of SUI episodes per day. If the pads are not worn for the entire time specified during a day, the fraction of the day the pads are worn will be used in computing the number of days. Therefore, there will be, say, 50 differences comprised of mean number of SUI episodes per day in the treatment period minus mean number of SUI episodes per day for control period. (These numbers will likely be negative.) The mean of these 50 mean differences represents the mean change in the number of SUI episodes per day from the control period to the treatment period. The null hypothesis will then be that the mean change in the number of SUI episodes is 0, and the alternative is that it is less than 0, analyzed using a paired t-test. A p-value of less than 0.0167 indicates success.

- b. For the quality of life score there will be three measures as described in the visit schedule above. For descriptive purposes the results and change from the previous visit will be shown, as well as the change from the enrollment visit to the post-treatment visit. The changes will likely be negative scores as the QOL is expected to improve, as the instrument records lower numbers as indicating a better quality of life. For the purposes of inferential analysis, a mixed model analysis of variance on the scores will be used on the result at time t (t=baseline, post-control, post-treatment) with time as a fixed effect and subject as a random effect. Thus, the null hypothesis is that there is no significant difference from baseline/enrollment to post-treatment, i.e., that the mean change in score is 0. The alternative is that this change is less than 0. Correlation of scores within subjects will be considered as compound symmetric. The p-value indicating the significance of the least square mean score at the third time-point compared to that at the first time-point will determine if the endpoint is met.

All inferential testing will be done on the mITT population and will be one-sided. As noted above statistical significance will be reached if the relevant p-value is less than 0.0167. Results for all populations will be reported.

There is a secondary safety endpoint as described earlier in the protocol. Safety reporting using urinalysis, vaginal swab, vaginal examination, and evaluation will be descriptive and narrative in nature.

Similarly, exploratory endpoint results of comfort and successful use will be descriptive. No inferential hypotheses will be used here.

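### Table 1 and the success limit in section 10.3 are set at one-sided 0.05, but section 10.4 tests each endpoint at 0.0167; Holm would serve three claims better than Bonferroni, and both sections should state one level

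*Combined protocol and SAP*

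**What the plan says.** Section 10.3 sets the planning level: "For power and sample size considerations a type 1 error rate (alpha) of 0.05, one-sided, will be used". Table 1 uses n=50 and a method that "computes a lower 95% confidence limit for the percentage change". The section closes by defining success for the primary endpoint as a lower 95% limit above 50%, with power above 90%.

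Section 10.4, item 1, explains that the sponsor wants to use success on pad weight, SUI episodes and quality of life for labeling and marketing, so "a Bonferroni adjustment for multiple comparisons will be employed". The same section repeats that "statistical significance will be reached if the relevant p-value is less than 0.0167", with all tests one-sided. For the primary endpoint it takes a lower limit at the 1 − 0.0167 level and compares it with the values found efficacious in section 10.3.

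On the planning assumptions, section 10.3 says that "this study's assumptions of 60% improvement and a range of standard deviations from 15% to 20% appear conservative". On the analysis set: "Sixty to seventy participants will be enrolled to allow for the fifty per-protocol participants, although the analyses will be done on the mITT population".

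**The concern.** The primary endpoint is planned at one level and decided at another. Section 10.4 refers back to section 10.3 for what counts as success, but the figures there were derived with a smaller critical value. Two things are at stake. First, some results would satisfy one section and fail the other, which leaves the primary conclusion open to argument. Second, the sponsor wants all three claims, yet Bonferroni holds every endpoint at 0.0167 even when the other two have succeeded. Holm's step-down procedure controls the same family-wise error without that restriction.

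**Working it through.** **Inputs.** From section 10.3: n=50, assumed mean reduction 60%, SD 15 to 20, half-widths 5 and 6, one-sided alpha 0.05. From section 10.4: null value 50%, one-sided 0.0167 per endpoint (0.05/3, rounded). The documents give no power or variance for the secondaries; the values used in step 4 are assumptions.

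**1. Reproducing Table 1.** The tabulated probability is that of a half-width no larger than w:

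P(t × s/√n ≤ w) = P(χ² on n−1 df ≤ (n−1) × [w√n/(t × SD)]²).

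With 49 df, t = 1.677 at one-sided 0.05 and 2.189 at 0.0167. For the first row at 0.05, 49 × [5 × 7.071/(1.677 × 16)]² ≈ 85.1, which gives 0.999. At 0.0167 the same expression is about 49.9, which gives 0.564.

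| Half-width | SD | Printed | Recomputed, 0.05 | Recomputed, 0.0167 |
|---|---|---|---|---|
| 5 | 16 | 0.999 | 0.999 | 0.564 |
| 5 | 17 | 0.991 | 0.991 | 0.334 |
| 5 | 18 | 0.956 | 0.957 | 0.167 |
| 5 | 19 | 0.869 | 0.872 | 0.073 |
| 5 | 20 | 0.720 | 0.726 | 0.028 |
| 6 | 20 | 0.995 | 0.995 | 0.405 |

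The printed table is therefore a one-sided 0.05 table. A two-sided 95% interval gives 0.850 for the first row and does not reproduce it. At 0.0167 no row reaches 90%. To keep the printed probabilities at n=50, the half-width of 5 would have to be about 6.5, and that of 6 about 7.8.

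**2. Power of the primary test.** One-sample noncentral t, 49 df, noncentrality (60 − 50)/(SD/√50), which is 4.42 at SD 16 and 3.54 at SD 20.

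| SD | Power at 0.05 | Power at 0.0167 |
|---|---|---|
| 16 | 0.997 | 0.986 |
| 18 | 0.987 | 0.956 |
| 20 | 0.967 | 0.907 |

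**3. Smallest observed mean that passes, SD 20.** The standard error is 20/√50 = 2.828.
- Section 10.3 limit, one-sided: 50 + 1.677 × 2.828 = 54.7%.
- Section 10.4 limit: 50 + 2.189 × 2.828 = 56.2%.

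Reading the section 10.3 interval as two-sided (t = 2.010) gives 55.7%, so a narrower gap would remain.

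**4. Chance that all three endpoints succeed.** Normal approximation, primary at 60% with SD 20, endpoints independent. Primary power at 0.0167 is Φ(3.536 − 2.127) = 0.92.
- Bonferroni, secondaries 95% powered at 0.0167: 0.92 × 0.95² = 0.83.
- Bonferroni, secondaries 80% powered: 0.92 × 0.80² = 0.59.
- Holm compares the smallest p-value with 0.0167, the next with 0.025 and the largest with 0.05, stopping at the first failure. Simulation gives 0.94 and 0.79 for the same two cases.

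**The case against.** The strongest reply is that nothing here is an error in type 1 control. Bonferroni is prespecified and justified, and 3 × 0.0167 = 0.0501 is 0.05 up to rounding. It lets each claim stand alone. That has value, because the primary must beat 50% while the secondaries need only beat zero change. All of this stands. It also answers the idea that a fixed sequence is plainly better: under a sequence, a missed pad-weight endpoint would block both secondary claims. The documents number the secondaries but state no testing order.

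The low Table 1 values are also easy to misread. A reader might infer that the trial is badly underpowered at 0.0167. The documents do not support that. The rows give the chance of a half-width of 5 or 6 points, whereas a true mean of 60% leaves 10 points above the null. Primary test power exceeds 90% over the whole SD range that the plan assumes. Moreover, n=50 is the per-protocol target and the analysis is on mITT, whose size is not stated. If it were 60, power at SD 20 would be 0.953 at 0.0167 and 0.985 at 0.05.

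A reader might also infer that Holm returns the full 0.05 to the primary. It does so only when both secondaries are rejected first; otherwise the primary is tested at 0.025 or 0.0167.

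What the reply does not remove is the mismatch between the two sections, or the fact that Holm keeps separate claims and never rejects less than Bonferroni.

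**Conclusion.** The concern holds as an inconsistency plus an avoidable loss of efficiency. Section 10.3 was not brought into line with section 10.4: Table 1 and the success limit belong to one-sided 0.05, and the decision is made at 0.0167. With SD 20 this leaves a band of observed means, 54.7% to 56.2%, in which the two sections disagree. The cost in primary power is modest at the plan's own assumptions: 0.967 to 0.907 at SD 20, and 0.997 to 0.986 at SD 16, with n=50.

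The larger gain from Holm is in the joint claim: 0.83 to 0.94, or 0.59 to 0.79. It depends on assumed secondary powers (95% or 80% at 0.0167) and independence. It does not support calling Bonferroni invalid or the primary endpoint underpowered.

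**What to change.** - In section 10.4, replace Bonferroni by Holm over the three endpoints at family-wise one-sided 0.05, and state the step-down thresholds 0.0167, 0.025 and 0.05.
- In section 10.3, restate Table 1 and the success limit at 0.0167, the level that Holm guarantees for the primary. Report test power against 50% beside the half-width probabilities so that the two are not confused.
- Let the Holm p-value rule decide success. Under Holm the primary's matching confidence limit depends on the other two tests, so a fixed 1 − 0.0167 limit could fall below 50% although the test succeeds. The bounds in section 10.6, after log transformation, need the same wording.

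An alternative is a fixed sequence at one-sided 0.05 (pad weight, then SUI episodes, then quality of life). Table 1 could then stand as printed. This is a trade-off for the sponsor, since a later endpoint could not be claimed after an earlier failure.

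If the sponsor keeps Bonferroni, the restatement of section 10.3 is still needed.

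The change needs no extra participants or data, but it should be made before results are seen. Sections 10.3 to 10.6 are protocol text, so it is a protocol amendment that needs IRB approval under section 13.2.
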